3. STUDY DESIGN

3.1. Summary of Study Design

This is an open-label, multi-center, single-arm, Phase 1 study evaluating the safety and pharmacokinetics of dinutuximab beta as maintenance therapy in Chinese patients with high-risk neuroblastoma.

Potential patients will be screened for eligibility before study enrollment (screening period ≤ 28 days). The study will recruit approximately 8 patients who will be hospitalized (with a full resuscitation equipment) on Day 1 of each cycle and will receive continuous infusion of dinutuximab beta administered at a dose of 10 mg/m²/day for 10 consecutive days in 35-day cycles (total dose 100 mg/m²/cycle). Patients must be administered in a unit with a full resuscitation equipment. Patients will be discharged from the hospital at the investigator's discretion. Patients will continue to receive 13-cis-RA 160 mg/m²/day, divided into close to 2 equal doses and given orally twice a day for 14 days after completion of dinutuximab beta infusion.

[figure not shown]
Patients may receive up to five 35-day cycles in the absence of relapse, disease progression or unacceptable toxicity.

Refer to Figure 1 for an overview of the study design and Appendix 1 for details on study assessments and procedures that will be carried out during the study.

The maximum duration of participation (Screening Visit to Safety Follow-up Visit) for individual patients will be approximately 35 weeks. Each patient will participate in the screening period (\leq 28 days), study intervention infusion period (\leq 25 weeks), and a post-infusion period (\leq 6 weeks). Additional clinical follow-up might be needed depending on findings during the study.

Figure 1: Study Schema

- Dinutuximab beta intravenous infusion (continuous infusion from Day 1 to Day 11 of each cycle)
- 13-cis-retinoic acid orally twice a day for 14 days, starting from the next day after completion of dinutuximab beta (Day 12 to Day 25) in each cycle

Abbreviations: EOT, end of treatment; PK, pharmacokinetic(s).

All patients will be closely monitored for AEs throughout the study and for 40 days after the last dose of study drug. AEs will be graded according to the NCI-CTCAE version 5.0. Refer to Section 9 for additional and specific information regarding AE monitoring and reporting.

PK analysis will be performed for dinutuximab beta.

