4.1. Inclusion Criteria

Each patient must meet all the following inclusion criteria to be considered eligible for participation in this study:

- 1. Signed informed consent form (ICF) and ability to comply with study requirements: patient or his/her parent/guardian must be capable of giving signed informed consent/assent as described in Section 14.3 including compliance with the requirements and restrictions listed in the ICF and in this protocol.
- 2. Age \geq 12 months at consent
- 3. Diagnosis of high-risk neuroblastoma according to the International Neuroblastoma Staging System (INSS) criteria, ie, INSS Stage 4 without *MYCN* amplification (MNA) and aged ≥ 18 months; or INSS Stage 2-4 with MNA
- 4. Patients who have previously received induction chemotherapy and achieved a partial or complete response followed by myeloablative therapy and stem cell transplantation. Stem cell transplantation should be completed within 120 days of dinutuximab beta first administration. The date patients complete the last stem cell transplantation is defined as day zero (Day 0).
- 5. Not receiving standard or experimental treatments within 2 weeks before study treatment start and full recovery from the short-term major toxic effects of any prior treatment
- 6. Consistency of contraceptive use by men or women with local regulations regarding the methods of contraception for those participating in clinical studies
 - NOTE: The reliability on sexual abstinence for male and/or female enrollment eligibility needs to be evaluated in relation to **the duration of the clinical study and the preferred and usual lifestyle of the patient**. Periodic abstinence (eg, calendar, ovulation, symptothermal, or postovulation methods) and withdrawal are not acceptable methods of contraception.
- 7. Females of childbearing potential must be willing to use a highly effective method of birth control for the duration of the study, and 180 days after the last dose of study drug(s), and have a negative urine or serum pregnancy test ≤ 7 days of the first dose of study drug(s) (Appendix 4).
- 8. Nonsterile males must be willing to use highly effective method of birth control for the duration of the study and for 180 days after the last dose of study drug(s) (Appendix 4).
 - A sterile male is defined as one for whom azoospermia has been previously demonstrated in a semen sample examination as definitive evidence of infertility.

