7.6. Discontinuation From Study Treatment or From the Study

7.6.1. Patient Discontinuation From Study Treatment (End of Treatment for an Individual Patient)

Patients have the right to discontinue study drug at any time for any reason. In addition, the investigator has the right to discontinue a patient from study drug at any time. Patients who discontinue study drug for reasons other than relapse or progressive disease (PD) should be followed for assessments of preliminary anticancer activity (Section 8.4) and safety (Section 8.2), if possible.

The primary reason for discontinuation from study drug should be documented on the appropriate eCRF. Patients may discontinue study drug for reasons including but not limited to the following:

- Relapse
- PD
- AE
- Patient decision
- Pregnancy
- Any medical condition that the investigator or sponsor determines may jeopardize the patient's safety if he or she were to continue the study drug
- Use of any concurrent anticancer therapy, including chemotherapy, hormonal therapy, immunotherapy, standard or investigational agents (including Chinese [or other Country] herbal medicine and Chinese [or other Country] patent medicines) for the treatment of cancer [regardless of cancer type])
- Patient noncompliance
 - Study site staff should first counsel patients who are significantly noncompliant (eg, missing 2 treatment cycles) on the importance of study drug compliance and drug accountability. The investigator may, in consultation with the medical monitor, discontinue patients from treatment who are consistently noncompliant.

Treatment with dinutuximab beta should be permanently discontinued if the following toxicities occur:

• Grade 3 or 4 anaphylaxis

- Prolonged Grade 2 peripheral motor neuropathy
- Grade 3 peripheral neuropathy
- Grade 3 vision eye toxicity
- Grade 4 hyponatremia (< 120 mEq/L) despite appropriate fluid management
- Recurrent or Grade 4 capillary leak syndrome (requires ventilator support)

If dinutuximab beta or 13-cis-RA is discontinued permanently before cycle 5 for reasons other than relapse or PD, the other drug could be continued per the study protocol.

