9.5.6. Recording Pregnancies

If a female patient or the partner of a male patient becomes pregnant while receiving study drug(s) or within 180 days after the last dose of dinutuximab, a pregnancy report form must be completed and expeditiously submitted to the sponsor to facilitate outcome follow-up. Information on the status of the mother and child will be forwarded to the sponsor. Generally, follow-up will be no longer than 6 to 8 weeks following the estimated delivery date. Any premature termination of the pregnancy will be reported.

While pregnancy itself is not considered to be an AE, any pregnancy complication or elective termination of a pregnancy for medical reasons will be recorded as an AE or SAE.

An abortion, whether accidental, therapeutic, or spontaneous, should always be reported as a SAE. Similarly, any congenital anomaly/birth defect in a child born to a patient exposed to the study drug(s) should be recorded and reported as a SAE.

9.5.7. Expedited Reporting to Health Authorities, Investigators, Institutional Review Boards, and Independent Ethics Committees

The sponsor will promptly assess all SAEs against cumulative study drug experience to identify and expeditiously communicate new safety findings to regulatory authorities, investigators, IRBs, and IECs based on applicable legislation.

To determine the reporting requirements for individual SAEs, the sponsor will assess the expectedness of the SAEs using the following reference safety information documents:

- Dinutuximab Beta's Prescribing Information
- local label of 13-cis-retinoic acid

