6.3. Data Analysis General Considerations

6.3.1. Definitions and Computations

Study drugs include dinutuximab beta and 13-cis-RA therapy.

Study day will be calculated in reference to the date of the first dose of study drug. For assessments conducted on or after the first dose, the study day will be calculated as assessment date – the first dose date + 1). For assessments conducted before the first dose, study day is calculated as (assessment date – the first dose date). There is no study day 0. In the situation where the event date is partial or missing, the date will appear partial or missing in the listings. Study day and any corresponding durations will be presented based on the imputations specified in Appendix 1.

Unless otherwise specified, a baseline value is defined as the last non-missing value collected before the first dose of study drug.

All calculations and analyses will be conducted using SAS® Version 9.4 or higher.

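### Pregnancy reporting runs from the last dinutuximab dose and contraception from the last dose of study drug(s), so a scheduled completer has 14 days of contraception with no pregnancy form required

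*Protocol*

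**What the plan says.** **Contraception.** Protocol Section 4.1 requires highly effective contraception in criterion 7 for females of childbearing potential ("for the duration of the study, and 180 days after the last dose of study drug(s") and in criterion 8 for nonsterile males ("for the duration of the study and for 180 days after the last dose of study drug(s").

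**Which drugs.** SAP Section 6.3.1 states: "Study drugs include dinutuximab beta and 13-cis-RA therapy". The protocol synopsis also lists both as investigational products.

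**Pregnancy reporting.** Protocol Section 9.5.6 requires a form, with follow-up of mother and child, for a pregnancy that begins "while receiving study drug(s) or within 180 days after the last dose of dinutuximab". The sentence names study drug(s) for the on-treatment period and one drug only for the period afterwards. Section 1.1 uses the bare name for the related SP2/0 product. Here it evidently means dinutuximab beta, and I read it so.

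**Order of dosing.** The schema in Protocol Section 3.1 gives dinutuximab beta as "continuous infusion from Day 1 to Day 11 of each cycle" and 13-cis-RA "starting from the next day after completion of dinutuximab beta (Day 12 to Day 25) in each cycle".

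**One drug without the other.** Under Protocol Section 7.6.1, if either drug "is discontinued permanently before cycle 5 for reasons other than relapse or PD, the other drug could be continued per the study protocol".

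**The concern.** Two rules that should cover the same exposure period start from different dates. The eligibility criteria count 180 days from the end of all study treatment. The reporting rule counts 180 days from the end of one component, and on the planned schedule that component finishes first. The protocol gives no reason for the difference. Section 9.5.7 names the 13-cis-RA label as reference safety information, so 13-cis-RA exposure does not appear to have been left out of safety reporting on purpose.

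At stake is the capture of an exposed pregnancy. Section 9.5.6 says pregnancy itself is not an AE, and general AE collection under Section 9.5.1 stops 40 days after the last dose. The schedule of assessments shows pregnancy tests at screening and on Day 1 of cycles, with none at the end-of-treatment or safety follow-up visits. Late after treatment, the form is therefore what starts outcome follow-up. Where no form is required, an uncomplicated pregnancy that began within the contraception period could go unrecorded.

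**Working it through.** **Inputs** (all from the protocol)
- Up to five cycles of 35 days (3.1)
- Dinutuximab beta ends on Day 11 of a cycle; 13-cis-RA runs Day 12 to Day 25 (3.1)
- Contraception: 180 days after the last dose of study drug(s) (4.1)
- Pregnancy form: while receiving study drug(s), or within 180 days after the last dinutuximab dose (9.5.6)

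**Check on the plan's own figures.** 5 × 35 / 7 = 25 weeks, as the synopsis states. 25 − 12 + 1 = 14 days of 13-cis-RA per cycle, also as stated.

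**Formulas**
- Study day = (cycle − 1) × 35 + cycle day
- Let D be the last dinutuximab beta day and R the last 13-cis-RA day, with R later than D.
- Uncovered days = (R + 180) − max(D + 180, R)
- The max term allows for the on-treatment clause, which keeps reporting open while 13-cis-RA is still being taken. It matters only if R − D exceeds 180. That never happens on the nominal schedule, so uncovered days = R − D.
- If dinutuximab beta is the last drug given, uncovered days = 0.

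**Completer on schedule**
- D = 4 × 35 + 11 = 151; the form requirement ends on 151 + 180 = Day 331
- R = 4 × 35 + 25 = 165; contraception ends on 165 + 180 = Day 345
- Uncovered: 345 − 331 = 14 days, or 14 / 180 = 8% of the window. The other 166 days are covered.
- Delays or the ±3-day Day 1 window move D and R together in Cycle 5, so the 14 days do not change.

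**13-cis-RA cut short or stopped first.** If the last 13-cis-RA dose falls on Cycle 5 Day 18, R = 158 and the gap is 158 − 151 = 7 days. If 13-cis-RA is stopped before dinutuximab beta, the gap is 0.

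**Dinutuximab beta stopped early, 13-cis-RA continued to Cycle 5 Day 25 (R = 165)**

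| Last full infusion | D | Uncovered days (165 − D) | Share of 180 |
|---|---|---|---|
| Cycle 4 | 116 | 49 | 27% |
| Cycle 3 | 81 | 84 | 47% |
| Cycle 2 | 46 | 119 | 66% |
| Cycle 1 | 11 | 154 | 86% |

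These rows need an assumption that the completer's result does not: that 13-cis-RA keeps its Day 12 to Day 25 position in cycles without an infusion. The protocol ties its start to the end of the infusion and gives no calendar for 13-cis-RA alone.

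**After the fix.** If 9.5.6 counts from the last dose of whichever study drug is given last, both windows end at R + 180, or at D + 180 when dinutuximab beta is last. The gap is then 0 in every row.

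**The case against.** **Other rules catch adverse outcomes.** This largely stands. Section 9.5.6 itself makes abortions SAEs, and also congenital anomalies in a child born to a patient exposed to study drug(s). It has pregnancy complications and medical terminations recorded as AEs or SAEs. Section 9.5.1 keeps related SAEs reportable without a time limit. It would be wrong to infer that nothing about a late pregnancy need be reported. What remains is the pregnancy with no such outcome. It triggers no form, so no prospective follow-up begins.

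**The long gaps are corner cases.** This also stands. A reader could stop dinutuximab beta on Cycle 1 Day 1, run 13-cis-RA to Day 165, and quote 165 − 1 = 164 uncovered days, giving a range of 14 to 164. The documents do not support that as a headline. Fourteen days is not a minimum, because the gap can be shorter or zero. The upper figure depends on the undocumented calendar for 13-cis-RA alone, and Section 7.6.1 only permits continuation.

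**The primary objective is not affected.** Agreed. A reader might argue that a missed pregnancy undermines the primary safety objective. The planned safety tables use TEAEs to 40 days after the last dose, or to new anticancer therapy if earlier (Protocol 10.2.2, SAP 6.6.2). Pregnancy is neither an AE nor an endpoint, so a conception on Days 332 to 345 enters no planned table under either wording.

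**Few patients are exposed.** About 8 are planned, and Section 1.1 says most patients are diagnosed before age 5. However, Section 4.1 sets no upper age limit, and 9.5.6 extends to partners of male patients. An event is unlikely but possible.

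**Conclusion.** The two sections are inconsistent as written, and the inconsistency touches the routine patient as well as early stoppers. For a scheduled completer, the last 14 of the 180 contraception days after treatment carry no requirement for a pregnancy form. That result rests only on the nominal schedule, on reading study drug(s) as both drugs (as the SAP defines them), and on 13-cis-RA being completed in the last cycle. The gap of about 49 to 154 days after an early dinutuximab beta stop is conditional on continuing 13-cis-RA at its nominal days through Cycle 5.

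The practical consequence is narrow: chiefly an otherwise uncomplicated exposed pregnancy, in a small and mostly young population. This is a minor safety-reporting inconsistency and leaves the planned analyses unaffected.

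**What to change.** In Protocol Section 9.5.6, count the 180-day reporting window from the last dose of study drug(s), meaning whichever of dinutuximab beta or 13-cis-RA is given last, so that it ends with the contraception window in criteria 7 and 8. If the sponsor intended different windows, the protocol should say so and give the reason.

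The cost is one phrase in the next amendment, with any matching change to the pregnancy form instructions. No dose, visit, test or contraception requirement changes, and the SAP needs no revision.

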9.5.8. Recording Infusion-Related Reactions

The symptoms of infusion-related reactions may include but are not limited to fever, chills/rigor, nausea, pruritus, angioedema, hypotension, headache, bronchospasm, urticaria, rash, vomiting, myalgia, dizziness, or hypertension. Severe reactions may include acute respiratory distress syndrome, myocardial infarction, ventricular fibrillation, or cardiogenic shock. Each of the individual signs and symptoms of an infusion reaction should be recorded as a separate AE in the eCRF and identified as an infusion-related reaction. Refer to the eCRF completion guidelines for details.

9.6. Risks Associated With Dinutuximab Beta

Hypersensitivity Reactions

Severe infusion-related reactions including cytokine release syndrome (CRS) and anaphylactic and hypersensitivity reactions may occur despite the use of premedication. Occurrence of a severe infusion-related reaction (including CRS) requires immediate discontinuation of dinutuximab beta therapy and may necessitate emergency treatment.

CRS frequently manifests itself within minutes to hours of initiating the first infusion and is characterized by systemic symptoms such as fever, hypotension, and urticaria.

Anaphylactic reactions may occur as early as within a few minutes of the first infusion with dinutuximab beta and are commonly associated with bronchospasm and urticaria.

Treatment of Hypersensitivity Reactions

Antihistamines, epinephrine (adrenaline), and prednisolone for intravenous administration should be immediately available at the bedside during administration of dinutuximab beta to manage life-threatening allergic reactions. Treatment for such reactions should include prednisolone and epinephrine administered by intravenous bolus every 3 to 5 minutes as necessary according to clinical response. In case of bronchial and/or pulmonary hypersensitivity reaction, epinephrine (adrenaline) inhalation is recommended and should be repeated every 2 hours according to clinical response.

Capillary Leak Syndrome

Capillary leak syndrome (CLS) is characterized by a loss of vascular tone and extravasation of plasma proteins and fluid into the extravascular space. CLS usually develops within hours after initiation of treatment, whereas clinical symptoms (ie, hypotension, tachycardia) are reported to occur after 2 to 12 hours. Careful monitoring of circulatory and respiratory function is required.

Neurological Disorders of The Eye

Eye disorders may occur as dinutuximab beta binds to optic nerve cells. No dose modification is necessary in the case of an impaired visual accommodation that is correctable with eyeglasses, as long as this is judged to be tolerable.

Treatment must be interrupted in patients who experience Grade 3 vision toxicity (ie, subtotal vision loss per toxicity scale). In case of any eye problems, patients should be referred promptly to an ophthalmology specialist.

Peripheral Neuropathy

Occasional occurrences of peripheral neuropathy have been reported with dinutuximab beta. Cases of motor or sensory neuropathy lasting > 4 days must be evaluated and non-inflammatory causes such as disease progression, infections, metabolic syndromes, and concomitant medication should be excluded.

Treatment should be permanently discontinued in patients experiencing any objective prolonged weakness attributable to dinutuximab beta administration. For patients with moderate (Grade 2) neuropathy (motor with or without sensory), treatment should be interrupted and may be resumed after neurologic symptoms resolve.

Systemic Infections

Patients are likely to be immunocompromised as a result of prior therapies. As they typically have a central venous catheter in situ, they are at risk of developing systemic infection. Patients should have no evidence of systemic infection and any identified infection should be controlled before starting therapy.

Hematologic Toxicities

Occurrence of hematologic toxicities such as erythropenia, thrombocytopenia, or neutropenia has been reported with dinutuximab beta. Grade 4 hematologic toxicities improving to \leq Grade 2 or baseline values by start of next treatment course do not require dose modification.

Laboratory Abnormalities

Regulatory monitoring of liver function and electrolytes is recommended.

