5.4. Dose Delay or Modification

Dose modification

This protocol allows some alteration from the currently outlined infusion schedule of dinutuximab beta, but the maximum cumulative exposure will not exceed 100 mg/m²/cycle.

Based on the Investigator's evaluation of the severity of adverse drug reactions to dinutuximab beta, patients may undergo a dose reduction of 50% or a temporary interruption of the infusion. As a consequence, either the infusion period is prolonged or, if tolerated by the patient, the infusion rate may be increased up to 3 mL/h (continuous infusion), in order to administer the total dose.

Regarding the dose modification of 13-cis-RA, please refer to local label of 13-cis-retinoic acid.

Table 3: Recommended Dinutuximab Beta Dose Modification

Adverse reaction	Severity	Treatment modification
Any	Grade 1 or 2	Decrease infusion rate to 50%. After resolution, resume infusion at original rate.

Hypersensitivity reaction	eg, Hypotension	Interrupt infusion and administer supportive measures. After resolution, resume infusion at original rate.
Dilated pupils with sluggish light reflex ± photophobia		Interrupt infusion. After resolution, resume infusion at 50% rate.
Any	≥ Grade 3	Interrupt infusion and administer supportive measures. Resume infusion at 50% rate if adverse drug reaction (ADR) resolves or improves to Grade 1 or 2 within 3 days of onset. If 50% dose reduction is tolerated for ≥ 1 day, consider advancing infusion to full rate as tolerated. If toxicity (≥ Grade 3) recurs at 50% dose reduction, treatment should be discontinued. If toxicity (≥ Grade 3) recurs while at 100% infusion rate, stop infusion and reduce dose to 50% if toxicity resolves or improves to ≤ Grade 2 within 3 days of onset. Do not increase dose to 100% again.
Capillary leak syndrome		Interrupt infusion and administer supportive measures. Resume at 50% rate if ADR resolves or improves to Grade 1 or 2.
Capillary leak syndrome requiring ventilator support; allergic reaction (anaphylaxis), skin toxicity, severe neuropathic pain, any other Grade 4 toxicity (which does not recover to Grade 1 or 2 or baseline within 5 weeks)	Grade 4	Discontinue infusion. Contact sponsor to confirm if patient may continue infusion at the start of the subsequent cycle.

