9.2.2. Assessment of Severity

The investigator will assess the severity for each AE and SAE reported during the study. AEs and SAEs should be assessed and graded based upon NCI-CTCAE version 5.0.

Toxicities that are not specified in NCI-CTCAE will be defined as follows:

- Grade 1: Mild; asymptomatic or mild symptoms; clinical or diagnostic observations only; intervention not indicated
- Grade 2: Moderate; minimal, local, or noninvasive intervention indicated; limiting age-appropriate instrumental activities of daily living
- Grade 3: Severe or medically significant but not immediately life-threatening; hospitalization or prolongation of hospitalization indicated; disabling; limiting self-care activities of daily living
- Grade 4: Life-threatening consequences; urgent intervention indicated
- Grade 5: Death related to AE

Note: The terms "severe" and "serious" are not synonymous. Severity is a measure of intensity (eg, grade of a specific AE, mild [Grade 1], moderate [Grade 2], severe [Grade 3], or life-threatening [Grade 4]); whereas, seriousness is classified by the criteria based on the regulatory

definitions. Seriousness serves as the guide for defining regulatory reporting obligations from the sponsor to applicable regulatory authorities as described in Section 9.5.2.

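### Section 9.6, Table 3 and Section 7.6.1 do not give one instruction for a severe (Grade 3) infusion or hypersensitivity reaction, and none says which governs

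*Protocol*

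**What the plan says.** Four places in the protocol bear on a severe reaction during the infusion.

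- **Section 9.6, under hypersensitivity reactions:** "Occurrence of a severe infusion-related reaction (including CRS) requires immediate discontinuation of dinutuximab beta therapy". No route back to treatment follows. CRS is described under the same heading and "is characterized by systemic symptoms such as fever, hypotension, and urticaria".
- **Section 5.4, Table 3, hypersensitivity row:** hypotension stands as the example where other rows show a grade. The action is "Interrupt infusion and administer supportive measures. After resolution, resume infusion at original rate".
- **Section 5.4, Table 3, row for any reaction of Grade 3 or above:** after interruption, "Resume infusion at 50% rate if adverse drug reaction (ADR) resolves or improves to Grade 1 or 2 within 3 days of onset".
- **Section 7.6.1:** "Treatment with dinutuximab beta should be permanently discontinued if the following toxicities occur". The list that follows includes "Grade 3 or 4 anaphylaxis". Neither CRS nor any other severe infusion-related reaction is on it.

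Table 3 also has a Grade 4 row that includes anaphylaxis. Its action is "Discontinue infusion. Contact sponsor to confirm if patient may continue infusion at the start of the subsequent cycle".

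**The concern.** An investigator with a patient in a Grade 3 reaction with hypotension can find three answers: stop therapy, interrupt and return to the original rate, or interrupt and return at half rate. These differ in whether the patient is exposed again and at what rate. Patients may be as young as 12 months, so this is first a question of patient safety.

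It is also a question of what the safety tables mean. Safety is a primary endpoint. Protocol Section 10.2.2 and SAP Section 6.6.2 count adverse events that led to discontinuation and interruption, and the SAP adds dose reduction. If the action taken reflects the page consulted as well as the reaction, those counts no longer describe tolerability alone. The trial has 1 to 3 centers and about 8 patients, so such differences will not average out.

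**Working it through.** The plan gives no figure to reproduce. The check is whether one event falls under several instructions, and whether anything ranks them.

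**Step 1: does a severe reaction enter the Grade 3 row?** Section 9.2.2 defines "Grade 3: Severe or medically significant but not immediately life-threatening". That scale is introduced for toxicities not specified in NCI-CTCAE, but the note below it pairs severe with Grade 3 in general terms. A severe reaction can therefore be read as Grade 3 and falls under the row for any reaction of Grade 3 or above.

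**Step 2: can it also enter the hypersensitivity row?** As the table reads, that row has no grade limit. Its example, hypotension, is among the symptoms of infusion-related reactions in Section 9.5.8 and of CRS in Section 9.6, where CRS sits under the hypersensitivity heading. Table 3 names neither CRS nor infusion-related reaction, so the overlap is by reading, not by name.

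**Step 3: set the instructions side by side for a Grade 3 reaction with hypotension.**

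| Place | Action | Restart |
|---|---|---|
| Section 9.6 | Discontinue therapy at once | None stated |
| Table 3, hypersensitivity row | Interrupt | Original rate, after resolution |
| Table 3, any reaction of Grade 3 or above | Interrupt | 50% rate, if improved within 3 days |
| Section 7.6.1 | Permanent stop if the event is anaphylaxis | Silent on CRS and other severe infusion reactions |

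The two Table 3 rows disagree with each other however Section 9.6 is read.

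**Step 4: is there a rule of precedence?** None is stated. Section 9.1.3 points to Section 9.6 for the measures meant to avoid or minimize anticipated toxicities, so Section 9.6 is operative text and not background. Table 3 makes no exception for the events that Section 9.6 names.

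**Step 5: anaphylaxis.** Section 7.6.1 ends treatment permanently for Grade 3 or 4 anaphylaxis, while the Grade 4 row of Table 3 leaves open continuation in the next cycle after contact with the sponsor. Anaphylaxis therefore belongs in the same reconciliation.

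**Step 6: size.** With 8 patients, one patient classified differently changes a rate by 1/8 = 12.5 percentage points. The frequency of severe reactions is not given.

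**The case against.** The strongest reply is that Section 9.6 need not mean the end of treatment. Where the protocol wants a final stop it uses the word permanently, in Section 7.6.1 and for prolonged weakness in Section 9.6 itself. Table 3 even couples discontinuing an infusion with possible continuation in the next cycle. This stands: a reader might infer that Section 9.6 orders permanent discontinuation and flatly contradicts Table 3, and the text does not go that far. But Section 9.6 speaks of therapy, uses interruption as a separate term for vision toxicity and Grade 2 neuropathy, and states when treatment may resume for that neuropathy but not here. Both readings remain open, and the choice between them decides re-exposure.

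Second, severe may mean something worse than Grade 3. The severe reactions listed in Section 9.5.8, such as ventricular fibrillation and cardiogenic shock, are life-threatening and lie nearer the Grade 4 row, which also discontinues the infusion. That narrows the conflict for those events. It does not remove it for a Grade 3 reaction, given the note in Section 9.2.2.

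Third, a named row may be taken to override a catch-all row. On that ordinary reading the apparent clash for Grade 1 or 2 hypersensitivity disappears, and it is not pressed here. Applied to Grade 3, the same convention would leave the original-rate instruction, which is no closer to Section 9.6, and the protocol does not state the convention. The table is broken in the text available, so a lost or merged severity cell in the hypersensitivity row cannot be excluded.

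Fourth, Table 3 is headed as recommended and rests on the investigator's judgment, whereas Section 9.6 says the stop is required. That is a hint of rank, not a rule. Section 15.3 restricts deviations in China without approval, so a site following one passage could be held to have departed from another.

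Fifth, the analysis absorbs part of the effect. SAP Section 6.7 uses actual dose and sampling times, the end-of-infusion sample follows an extended infusion, and reasons for dose changes are recorded. This largely answers any claim that the PK parameters would be miscalculated. It does not make the action counts comparable between sites.

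**Conclusion.** The point holds as an unresolved inconsistency. For a Grade 3 infusion or hypersensitivity reaction, Section 9.6 requires a stop of unstated duration, Table 3 offers two different restart rates, Section 7.6.1 is silent unless the event is anaphylaxis, and nothing ranks them. It rests on reading severe as Grade 3 and on the hypersensitivity row having no grade limit, as it appears.

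Two stronger inferences are not supported. One is that Table 3 sends a patient with CRS back to full rate: the table does not name CRS, and hypotension is also a sign of capillary leak syndrome, which has its own row. The other is that most patients will meet the conflict. Section 1.2.3 reports hypersensitivity in 63% of patients, or 8 × 0.63 = 5.04 of 8, but that figure includes pyrexia and pruritus and gives no severe share. The chance of at least one severe case in 8 is 1 − (1 − p)^8, which is 34%, 57% or 83% for assumed p of 5%, 10% or 20%; the range reflects only the assumption. The case for correction does not depend on it.

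The consequence that can be stated is a 12.5-point shift per patient in a discontinuation or interruption rate, and re-exposure decided by the passage read. Because that concerns patient safety, it should be settled in the text.

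**What to change.** Reconcile Section 9.6, Table 3 and Section 7.6.1 so that each grade of hypersensitivity reaction, infusion-related reaction, CRS and anaphylaxis leads to one instruction. State which passage or row governs where they overlap. State whether discontinuation in Section 9.6 means the current infusion or all further treatment. The sponsor's clinical team decides the content; no clinical rule is proposed here.

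The cost is a wording amendment to three places in the protocol, with the usual approvals. It adds no procedure, visit or patient, and the analyses in the SAP stay as they are.
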